# 12.8. Exploratory Analyses

Additional, ad hoc exploratory analyses may also be conducted.

# 12.9. Sex Analysis

Potential differences between genders in the primary endpoint success rate will be evaluated. The primary endpoint success rate will be calculated and presented for each sex. A comparison between the sex will be made using Fisher's exact test.

# 12.10. Gap Measurement Analysis

Gap measurements will be collected on all devices. During assembly of the Pyrocarbon humeral head onto the male taper a "gap" measurement is used to determine the acceptability of component tolerancing prior to assembly. The gap measurements will be summarized using descriptive statistics, including median and interquartile range. A subgroup analysis will be performed where the primary endpoint will be summarized by quartiles of the gap measurements. A comparison between the subgroups will be made using Fisher's exact test.

# 12.11. Safety Analysis

All adverse events and deaths will be reported and summarized. This includes all operative procedure and postoperative complications. Events are categorized as device-related, procedure-related) and systemic (non-device or procedure related). An event is considered related if the investigator indicated it was definitely or possibly related.

Safety analyses will be performed on the ITT population. The objective of the safety analysis is to demonstrate that the investigational system has an acceptable safety profile. Adverse events will be summarized by the proportion of subjects with serious adverse events, device-related adverse events and unanticipated adverse device effects (from adjudication), and also by the individual AE terms. Additionally, a summary will be presented according to the FDA guidance Clinical Data Presentations for Orthopedic Device Applications (2004), separating events by category (device-related, procedure-related, systemic) and by time period. The denominator for the time periods will include all subjects who were evaluated at some point during the time period (scheduled visit or AE within window). The number of occurrences of each type of adverse event within the visit window will be presented. For this analysis, visits are defined as follows, using the upper end of the planned visit windows from the protocol:

- Operation: day of procedure (Day 1)
- Post-op: Day 2 to Day 21
- 3 months (12 weeks): Day 22 Day 105
- 6 months (26 weeks): Day 106 Day 203
- 12 months (52 weeks): Day 204 Day 392
- 24 months (110 weeks): ≥Day 393
- A total column may also be added

Subsequent secondary surgical interventions will be presented similarly to the above adverse event description following the FDA guidance Clinical Data Presentations for Orthopedic Device Applications (2004), using the following surgical categories: revisions, removals, reoperations, and other, as applicable. This table may be generated manually.

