7.1 Overview of Study Design

Figure 5 outlines the study overview and subject flow. Subjects who are screened and provided informed consent are considered enrolled and will complete a pre-operative baseline study assessment.

Subjects who are enrolled and have a successful implant attempt (implant stable through wound closure) will have study assessments at 2 weeks, 3 months, 6 months, 12 months, 24 months, and annually thereafter (until the last subject with an implant attempt completes their 24 month visit or is determined lost to follow-up) following surgery. Subjects will exit the study after the last subject with an implant attempt completes their 24 month visit or follow subjects their 24 month assessment unless it is determined, at the end of the study, to follow subjects long-term.

Subjects who are enrolled and have an unsuccessful implant attempt (attempt to implant the Pyrocarbon Humeral Head was not successful during the index procedure) will have annual post-op visits at 12 and 24 months in order to collect any available safety information. This also includes subjects who are excluded due to excessive glenoid reaming performed with the intent of implanting the Pyrocarbon Humeral Head. Subjects will exit the study after the 24 month assessments are complete.

Subjects who are enrolled but become screen failures intra-operatively (prior to the implant attempt) will have the reason for screen failure documented and then will be followed annually to collect any available safety information. Subjects will exit the study after the 24 month assessments are complete.

Subjects who are enrolled but become screen failures pre-operatively (prior to surgical procedure) will have the reason for screen failure documented then will be exited from the study.

If any component of the investigational system is revised, the subject will follow the planned follow-up visits. If any component of the investigational system is permanently explanted during the course of the study, the subject will only have annual post-op visits at 12 and 24 month to gather available safety information. Revisions and explants are defined in section 7.7

[figure not shown]

Figure 5: Study Overview

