7.6.9 Follow-up: Unsuccessful Implant Attempt

Reason for the unsuccessful implant attempt will be documented on the surgical form. Subjects will be seen at 12 and 24 months to gather available safety information. These visits may occur over the phone if the subject is unable to attend in person. Subjects will be exited after the 24 month visit.

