7.7 Additional Data Collection

Subjects may call or visit the investigative site at times other than for required study visits. It is only required to notify Tornier if the visit or phone call is associated with an adverse event, revision, device explant, reoperation, device malfunction, subject death, or study exit. Data associated with these events must be documented and reported in the database on the associated eCRFs.

Revision and Device Explants

A revision is a procedure that adjusts or in any way modifies or removes any component of the original implant configuration, with or without replacement of a component, after the initial surgery. A revision may also include adjusting the position of the original configuration.

An explant is a revision that includes permanent removal of any system component. If a subject has a revision that includes an addition of a glenoid component (revision to TSA) the Pyrocarbon humeral head must be permanently explanted.

All explanted system components, including the Pyrocarbon HH devices and stems, must be returned to Tornier for analysis per the system retrieval and analysis protocol in Appendix 4.

Reoperation

A reoperation is any invasive procedure to the affected shoulder that does not include removal, modification or addition of any components to the original implant configuration (e.g., drainage of a hematoma at the surgical site). Subjects will not be considered a failure solely due to a reoperation and will follow their original follow-up schedule.

Device Malfunction

All failures and malfunctions of the implant system must be reported to Tornier as soon as possible. In the event of a system malfunction, every effort must be made to return the suspected system to Tornier for analysis.

Death

During the study, all deaths must be reported to the Sponsor within 10 working days of the study personnel's knowledge of the death. A copy of death records, medical records for the events that led to the subject's death, death certificate (if available) and an autopsy report (if performed) must be sent to the Sponsor as soon as they become available.

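### The by-period adverse event table counts a subject without a visit in the period only if that subject had an event, so its rates lean upward

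*SAP*

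**What the plan says.** SAP 12.11 sets the population first: "Safety analyses will be performed on the ITT population". ITT includes every subject with an attempted implant, successful or not. The main summary follows: "Adverse events will be summarized by the proportion of subjects with serious adverse events, device-related adverse events and unanticipated adverse device effects". No period denominator is attached to it.

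A second display is then added: "Additionally, a summary will be presented according to the FDA guidance Clinical Data Presentations for Orthopedic Device Applications (2004". It splits events by category and by period, from the day of operation to an open-ended 24-month period. For this display only, the denominator is to "include all subjects who were evaluated at some point during the time period (scheduled visit or AE within window". On content the SAP says: "The number of occurrences of each type of adverse event within the visit window will be presented". The table of later surgical interventions is to be laid out in a similar way.

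The visit schedule matters here. For unsuccessful implant attempts, Protocol 7.6.9 says: "Subjects will be seen at 12 and 24 months to gather available safety information". After a permanent explant, Protocol 7.1 says "the subject will only have annual post-op visits at 12 and 24 month to gather available safety information". On contacts outside the schedule, Protocol 7.7 says "It is only required to notify Tornier if the visit or phone call is associated with an adverse event" or another listed event. An event-free call therefore need not reach the database, and could not qualify a subject as evaluated.

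**The concern.** A denominator should be fixed without looking at the outcome. Here a subject under follow-up who has no visit in a period is in the denominator with an event and out of it without one. Every such case enters both numerator and denominator; every such non-case enters neither. The subject rate can only move up.

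The displacement is also uneven. It is zero on the day of surgery, when every ITT subject is seen, and grows in periods where fewer subjects have a visit. A by-period table exists to show how risk changes over time, so an error that follows attendance blurs what the table is for. If the similar layout carries the rule over, the same applies to revisions, removals and reoperations by period.

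**Working it through.** **1. The plan's own figure.** The documents state no adverse event rate and no period denominator. The base they do give is 157 implant attempts, which is the planned ITT size. It reproduces: n = [1.960·√(0.75·0.25) + 0.842·√(0.85·0.15)]² / 0.10² = 132.07, so 133; and 133/0.85 = 156.5, so 157.

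**2. Who can lack a visit in a period.**
- Subjects who miss a scheduled visit but remain in follow-up.
- Unsuccessful implant attempts, in the post-op, 3-month and 6-month periods (study days 2 to 203).
- Explanted subjects, in any of those periods that lies wholly after the explant.
- Possibly, subjects seen on time. The SAP periods end on days 105, 203 and 392 with surgery as day 1. The protocol windows end on days 111, 201 and 407 with surgery as day 0. If visits are placed by date, 7 of the 43 allowed days for the 3-month visit (study days 106–112) and 16 of the 85 for the 12-month visit (study days 393–408) fall into the next period. If visits are placed by their CRF label, as SAP 11.3 does for time-point data, this group disappears and the others remain.

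**3. Formula.** Let N subjects be at risk, a share v have a visit, and e be the true subject-level risk, equal in both groups and fully captured.
- Numerator: N·e
- Denominator under the rule: N·v + N·(1−v)·e
- Table rate: e / [v + (1−v)e]

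The ratio to the true rate is 1/[v + (1−v)e], which is below 1/v. The relative error is therefore below 1/v − 1: 5.3% at v = 0.95, 11.1% at 0.90 and 17.6% at 0.85.

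**4. Results.** Both v and e are assumed, because the documents give neither visit attendance nor event risk.

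| v | e = 5% | e = 10% | e = 20% |
|---|---|---|---|
| 1.00 | 5.0% | 10.0% | 20.0% |
| 0.95 | 5.25% | 10.5% | 20.8% |
| 0.90 | 5.5% | 11.0% | 21.7% |
| 0.85 | 5.8% | 11.6% | 22.7% |

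Example: e = 10%, v = 0.85 gives 0.10/(0.85 + 0.015) = 0.10/0.865 = 11.6%.

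**5. Incomplete capture.** If events in subjects without a visit are captured at a fraction r of the normal rate, the table shows [ve + (1−v)er] / [v + (1−v)er]. At v = 0.85 and e = 10%:
- r = 0.5: 0.0925/0.8575 = 10.8%. Dividing by all at risk would give 9.25%.
- r = 0: 0.085/0.85 = 10.0%. Dividing by all at risk would give 8.5%.

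**6. The part built into the schedule.** The number of unsuccessful attempts is not given. Assume 5 of 157, all others attending, and e = 10%: 15.7/(152 + 0.5) = 10.3%.

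**The case against.** The strongest reply is about scope. The rule governs one additional display, which the SAP describes by numbers of occurrences without a percentage formula. That limits the point but does not remove it, since a denominator has no use unless a rate is shown or implied.

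The second reply is that the error runs against the device and is modest at good attendance. Both stand. The unevenness across periods stands as well.

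The third is that an at-risk denominator has its own bias. It treats unobserved subjects as event-free, and Protocol 7.8 asks for three documented contact attempts before a subject is declared lost, so formal exit can lag true loss. Step 5 shows this is real: with no capture among non-attenders, the SAP rule is right and the at-risk rate is low. The remedy is to end time at risk at last contact, so that subjects who are out of reach do not stay in the denominator.

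The fourth is that the format follows an FDA guidance. Its text is not available here, so whether it prescribes this denominator cannot be judged.

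A reader might also infer more than the documents support:
- *That the trial's adverse event rates are wrong in general.* The overall ITT proportions do not use this denominator.
- *That the revision test is affected.* SAP 12.6 bases it on a Kaplan-Meier estimate.
- *That the plan's 15% attrition sets v = 0.85.* That figure is loss of evaluable primary endpoint data by 24 months. Much of it would be subjects who have left the study, and those without an event in the period are outside the denominator under either rule.
- *That explanted subjects appear in every early period only as cases.* They keep the full schedule until the explant.

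**Conclusion.** The defect in the rule is certain as written; its size is not. By-period subject rates in the supplementary table are biased upward whenever some at-risk subjects have no visit and report events. Under full capture and equal risk, a true 10% would read between 10.5% and 11.6% for v between 0.95 and 0.85. There is no distortion if everyone is seen in the period or if non-attenders report no events. Within the subgroup that has no early visits the rate is 100% by construction, but the SAP does not report that subgroup separately, and it may be small.

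The primary endpoint and the main safety proportions are untouched. Carry-over to the surgical intervention table is a reasonable reading of the layout instruction, not an explicit rule. Severity is minor: a descriptive table with an outcome-dependent denominator that is easy to put right.

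**What to change.** Replace the denominator sentence in SAP 12.11 with one to this effect: for each period, the denominator is all ITT subjects still in follow-up on the first day of that period, meaning not dead, not exited and not past last contact, regardless of visit attendance or adverse event status. Use subjects with at least one event in the period as the numerator, and show event counts beside it. State that the same rule applies to the secondary surgical intervention table.

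Take last contact from study visits, including those allowed by telephone, and from exit or death records. If event reports alone could extend it, the dependence on the outcome would return for subjects otherwise lost. List any event reported after last contact separately. The remaining downside is that a subject lost but not yet formally exited may count briefly as event-free, which the last-contact date limits.

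While the section is open, reconcile the period ends (days 105, 203 and 392) with the protocol windows they are said to follow, and surgery as day 0 with surgery as day 1.

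The cost is one SAP sentence and a small programming change. Visit, exit and death data are already collected, so no new data are needed.

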7.4 Data Collection

The study data that will be collected at each visit is listed in Table 3. Data will be submitted to Tornier via an Electronic Data Capture (EDC) system using electronic Case Report Forms (eCRFs). Worksheets will be provided to investigative sites to aid in data collection during subject visits. Data should be entered into the database in a timely manner. Queries will be issued via the EDC system as a part of data quality assurance and monitoring.

	Baseline (Pre-op)	Day of Surgery (DOS)	Post-op Follow-up (5-21 days)	Follow-up 3M (69-111 days)	Follow-up 6M (159-201 days)	Follow-up 12M (323-407 days)	Follow-up 24M (688-772 days)	Follow-up Annual (if applicable)
Demographics,	Х							
Medical History and								
Indication								
Intraoperative Data		Х						
Subject Questionnaire	Х			Х	Х	Х	Х	Х
Range of Motion	X			X*	X*	Х	Х	Х
Strength Test	Х			X*	X*	Х	Х	Х
Pain Medications	X	Х	Х	Х	Х	Х	Х	Х
Adverse Event		Х	Х	Х	Х	Х	Х	Х
Assessment								
X-ray	Х		Х		Х	Х	Х	Х

Table 3:	Data	Collection	Overview
----------	------	------------	----------

*Optional

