7.5 Subject Follow-up Schedule

Visit windows are provided to allow scheduling flexibility. Subject follow-up visits or procedures that do not occur in the windows listed in Table 4 will be considered a study deviation and require completion of a study deviation form. The day of surgery (DOS) is considered day zero. The baseline visit is preferred to occur as close as possible to the surgery and must be within 60 days prior to surgery.

Study Visit	Visit Window		
Baseline	60 days pre-op through DOS		
Post-op Follow-up	5-21 days post-op		
3 Month Follow-up	90 Days post-op ± 21 days		
6 Month Follow-up	180 Days post-op \pm 21 days		
12 Month Follow-up	365 Days post-op \pm 42 days		
24 Month Follow-up	730 Days post-op \pm 42 days		
36 Month Follow-up (if applicable)	1095 Days post-op \pm 84 days		
48 Month Follow-up (if applicable)	1460 Days post-op \pm 84 days		
60 Month Follow-up (if applicable)	1825 Days post-op \pm 84 days		
72 Month Follow-up (if applicable)	2190 Days post-op \pm 84 days		

 Table 4: Visit Windows

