Subjects who are enrolled but become screen failures intra-operatively (prior to the implant attempt) will have the reason for screen failure documented and then will be followed annually to collect any available safety information. Subjects will exit the study after the 24 month assessments are complete.

Subjects who are enrolled but become screen failures pre-operatively (prior to surgical procedure) will have the reason for screen failure documented then they will be exited from the study.

If any component of the investigational system is revised, the subject will follow the planned follow-up visits. If any component of the investigational system is permanently explanted during the course of the study, the subject will only have annual post-op visits at 12 and 24 month to gather available safety information. Revisions and explants are defined in section11.2.

	Baseline (Pre-op)	Day of Surgery (DOS)	Post-op Follow-up (5-21 days)	Follow-up 3M (69-111 days)	Follow-up 6M (159-201 days)	Follow-up 12M (323-407 days)	Follow-up 24M (688-772 days)	Follow-up Annual (if needed)
Demographics, Medical History and Indication	х							
Intraoperative Data		Х						
Subject Questionnaire	Х			Х	Х	Х	Х	х
Range of Motion	Х			X*	X*	Х	Х	Х
Strength Test	Х			X*	X*	Х	Х	Х
Pain Medications	Х	Х	Х	Х	Х	Х	Х	Х
Adverse Event Assessment		Х	х	Х	х	Х	Х	X
X-ray	Х		Х		Х	Х	Х	Х

Data collection schedule is as follows:

\*Optional

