# 11.3. Visit Windows

All data attributed to a time point per the CRF will be included in the analysis of that time point, regardless of whether it is out of the protocol specified window. A summary of visit-window adherence will be included in the final analysis. Unscheduled visit data will be included in adverse event and other summaries that are not specific to a time point. The table below outlines the visit windows for protocol prescribed visits.

Study Visit	Visit Window
Baseline	60 days pre-op through DOS
Post-op Follow-up	5-21 days post-op
3 Month Follow-up	90 Days post-op $\pm 21$ days
6 Month Follow-up	180 Days post-op $\pm$ 21 days
12 Month Follow-up	365 Days post-op $\pm$ 42 days
24 Month Follow-up	730 Days post-op $\pm$ 42 days
36 Month Follow-up (if needed)	1095 Days post-op $\pm$ 84 days
48 Month Follow-up (if needed)	1460 Days post-op $\pm$ 84 days
60 Month Follow-up (if needed)	1825 Days post-op $\pm$ 84 days
72 Month Follow-up (if needed)	2190 Days post-op $\pm$ 84 days

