### 12. Statistical Analyses

### 12.1. General Considerations

Data will be summarized using descriptive statistics. Continuous data will be summarized using mean, standard deviation, minimum, and maximum. Where appropriate, non-parametric measures of location (e.g. median, interquartile range) may be provided. For categorical data frequencies and percentages will be provided.

The surgery date will be considered study day 1.

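### The adverse-event time bins in SAP 12.11 are not the protocol window ends they claim to be, and the 24-month bin has no upper limit

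*SAP*

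**What the plan says.** SAP 12.11 plans a by-period summary of adverse events and gives the rule for its periods: "For this analysis, visits are defined as follows, using the upper end of the planned visit windows from the protocol". The periods listed are:

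- Operation: Day 1
- Post-op: Day 2 to 21
- 3 months (12 weeks): Day 22 to 105
- 6 months (26 weeks): Day 106 to 203
- 12 months (52 weeks): Day 204 to 392
- last row: "24 months (110 weeks): ≥Day 393"

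The same periods set the denominators: "The denominator for the time periods will include all subjects who were evaluated at some point during the time period", where evaluated means a scheduled visit or an adverse event inside the period. Secondary surgical interventions are to be tabulated in a similar way.

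The windows stand in four places that agree with one another: Protocol 7.4 (Table 3), Protocol 7.5 (Table 4), the schedule in SAP 9, and SAP 11.3. Examples are "Follow-up 3M (69-111 days" in the protocol and "Follow-up 12M (323-407 days" in the SAP.

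The two documents number days differently. Protocol 7.5 says: "The day of surgery (DOS) is considered day zero". SAP 12.1 says: "The surgery date will be considered study day 1".

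Protocol 2.2 and 7.6.6 and SAP 9 have implanted subjects seen annually after month 24, with adverse-event assessment, until the last implant-attempt subject reaches the 24-month visit. Windows are listed out to 72 months.

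**The concern.** The rule in SAP 12.11 and the list below it disagree. A programmer who codes the list will not produce the table that the text describes. Three things follow.

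1. **Misplaced visits and events.** A subject seen late but inside the 3- or 12-month window is counted in the following period, as are adverse events on those days.
2. **Denominators.** A subject whose 12-month visit falls on SAP Day 393 to 408 has no other in-window scheduled visit in the 12-month bin, because the 6-month window closes on SAP Day 202 and the bin opens on Day 204. Without an adverse event in that bin, the subject leaves the 12-month denominator and enters the 24-month one, even if lost before month 24. The loss is selective: these subjects were at risk and event-free throughout Day 204 to 392, so dropping them overstates the proportion with an event in that period.
3. **An unlimited last column.** Events at month 30 or 36 appear under a 24-month heading. A month-30 revision would sit in the 24-month column of the surgical table but not in the within-24-month revision summaries of SAP 12.6, so one report could show two different 24-month revision counts.

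The general rule in SAP 11.3, "All data attributed to a time point per the CRF will be included in the analysis of that time point", does not prevent this, because 12.11 redefines visits by day for this analysis.

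**Working it through.** **Step 1. Apply the stated rule.** Upper end = target day + half-width (Protocol Table 4; SAP 11.3). Because the SAP calls surgery Day 1, SAP Day = post-op day + 1.

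| Visit | Window, post-op days | Upper end | As SAP Day | End listed in 12.11 |
|---|---|---|---|---|
| Post-op | 5–21 | 21 | 22 | 21 |
| 3 months | 90 ± 21 = 69–111 | 111 | 112 | 105 |
| 6 months | 180 ± 21 = 159–201 | 201 | 202 | 203 |
| 12 months | 365 ± 42 = 323–407 | 407 | 408 | 392 |
| 24 months | 730 ± 42 = 688–772 | 772 | 773 | none |

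The listed ends are not reproduced under either numbering, except the post-op end when surgery is taken as day 0.

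**Step 2. Look for a rule that gives the listed ends.** Week-based arithmetic does: 12×7 + 21 = 105, 26×7 + 21 = 203 and 52×7 + 28 = 392. The 110-week label is 110×7 = 770 = 104×7 + 42. These are not the current windows; in particular, the 12-month half-width is 42 days, not 28. They may be left over from another set of windows. That is inference, and nothing below depends on it.

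**Step 3. Count misplaced in-window days.** On the post-op scale the SAP bins are days 1–20, 21–104, 105–202, 203–391 and 392 onward.

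- 3 months: days 105–111 fall in the 6-month bin, 7/43 = 16%. With surgery as day 0: 6/43 = 14%.
- 12 months: days 392–407 fall in the 24-month bin, 16/85 = 19%. With surgery as day 0: 15/85 = 18%.
- 6 months: the end differs by one or two days and no in-window visit moves.
- Post-op: day 21 moves to the 3-month bin under the SAP's numbering only.
- 36 and 48 months: all 169 days of each window (1095 ± 84 and 1460 ± 84) fall in the 24-month bin.

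**Step 4. Illustrate the 12-month denominator.** The documents do not give visit timing, so it is assumed here. Take 157 subjects, all with an in-window 12-month visit, and find the share on post-op days 392–407. For the normal cases, visits centre on day 365 and are truncated to the window.

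| Assumed timing | Share | Of 157 |
|---|---|---|
| Normal, SD 14 days | 0.028 | 4.4 |
| Normal, SD 21 days | 0.086 | 13.4 |
| Uniform over the window | 16/85 = 0.188 | 29.6 |

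**Step 5. Illustrate the open last bin.** Assume uniform accrual over A days and a study end when the last subject reaches day 730. A subject entering u days before the last one is followed to day 730 + u.

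- Mean person-time from post-op day 392: 339 + A/2.
- Mean person-time after day 772: (A − 42)²/(2A).
- A = 547.5 (18 months, protocol synopsis): 233/613 = 0.38.
- A = 730 (24 months, Protocol 2.2): 324/704 = 0.46.
- With exponential dropout reaching 15% at day 730 (the planned attrition): 0.36 and 0.44.

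**The case against.** The strongest reply is that little is lost. The bins are contiguous and exhaustive, so each event is counted once and none disappears. Numerators and denominators use the same bins, and a subject seen on Day 400 was indeed evaluated in the period that starts on Day 393. The last row shows openly that it has no upper limit. On this view only the sentence about where the cut-points came from is wrong.

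The observation about counting is right, but the conclusion does not follow. Readers will take the columns as visit periods, and the SAP says they are. The denominator effect is real for subjects who kept to the schedule.

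Several qualifications to the figures stand:

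- An out-of-window 6-month visit on or after SAP Day 204 also keeps a subject in the 12-month denominator.
- The 16% and 19% are shares of visit-window days. As shares of bin length the displacement is smaller: against the corrected bins, 7/90 for the 3-month bin and 16/206 for the 12-month bin, about 8% each.
- The counts out of 157 assume full attendance. On the 133 evaluable subjects the same shares give about 4, 11 and 25. Nothing in the documents supports uniform timing, so the largest count is an upper illustration.
- The 36–46% is person-time, which the table does not report. It equals a share of events only if the event rate is constant. It also follows every subject to study end, whereas subjects with an unsuccessful attempt exit at 24 months and explanted subjects have reduced follow-up.
- Removing the week labels is partly presentation. The FDA guidance that the table follows was not available for this check, and the surgical table may be produced by hand.

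**Conclusion.** The point holds. On the text alone, SAP 12.11 contradicts the protocol windows and the SAP's own tables, under either day numbering, at the 3- and 12-month ends. The last bin also files all later follow-up under 24 months. Under the SAP's numbering, 7 of 43 in-window days for the 3-month visit and 16 of 85 for the 12-month visit go to the wrong period; this needs no assumption. The 4 to 30 subjects moved at 12 months, and the 36–46% of the last bin's person-time that lies after the 24-month window, rest on the assumed visit timing, accrual and dropout, and only illustrate scale.

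The reach is narrow: two descriptive by-period tables with no decision rule attached. The primary non-inferiority test, the revision analyses in SAP 12.6 and the overall adverse-event proportions are unaffected. It should be corrected because the error is certain, the tables support the safety assessment, and the correction is cheap.

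**What to change.** In SAP 12.11, replace the list of periods with:

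| Period | SAP Days |
|---|---|
| Operation | 1 |
| Post-op | 2–22 |
| 3 months | 23–112 |
| 6 months | 113–202 |
| 12 months | 203–408 |
| 24 months | 409–773 |
| After 24 months | 774 onward |

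State there that SAP Day equals protocol post-op day plus 1. Remove the week labels, which do not match the windows. Apply the same periods to the secondary surgical intervention table.

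Check of the fix: in SAP Days the five windows are 6–22, 70–112, 160–202, 324–408 and 689–773, and each lies wholly inside its own period.

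The cost is a change of SAP wording and programming constants, plus one extra column in two tables. The protocol and data collection stay as they are.
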